#### PFIZER CONFIDENTIAL

The third party responsible for performing medical record review must obtain Pfizer's written permission before disposing of any records, even if retention requirements have been met.

### 9.7. Data Analysis

Detailed methodology for summary and statistical analyses of data collected in this study will be documented in a statistical analysis plan (SAP), which will be dated, filed and maintained by the sponsor. The SAP may modify the plans outlined in the protocol; any major modifications of primary endpoint definitions or their analyses would be reflected in a protocol amendment.

All data analyses will be performed separately for each data source, and an analysis to pool data at the aggregate level between Swedish and HIRD data sources will be conducted (see Section 9.7.5 Pooled Analyses).

# 9.7.1. Propensity Score Matching

Details of the statistical methods for PS estimation and matching will be described in the statistical analysis plan. To control for confounding factors, PS will be constructed from baseline covariates for all cohort comparisons. The PS is the estimated probability of receiving a study drug dispensing (i.e., LDVE, MDVE, HDVC), conditional on a set of observed covariates. Propensity scores will be estimated with covariate information collected during the baseline period for each group and each comparison using logistic regression models. Covariates selected will be variables that are related to the outcome, based on literature and clinical judgment as well as sufficiently prevalent in the population to bias the associations under study. Baseline variables to be considered in the model for computing PSs will include demographics, clinical comorbidities, medication use, duration of prior use of hormone therapy, and healthcare utilization (see Section 9.3.4 Baseline Covariates). Propensity score models will also consider for inclusion the 25 most frequently occurring diagnoses, procedures, and medications within the past 12 months among exposed women in the study population that will be ascertained separately in each database. Inclusion of these diagnoses, procedures, and medications in the PS analysis will be based on evidence of association with endometrial cancer in the literature and prevalence.

Comparison groups will be individually matched to exposure groups according to PS to balance the exposure and comparator group on baseline risk factors for outcome at cohort entry. Based on sample size estimates, a matching ratio of 1:4 exposed (e.g., LDVE) to comparator patients (e.g., non-users) is planned. If a 1:4 matching ratio is not possible, 1:3 will be tried, and so on.

The PS matched groups will be evaluated for balance and any patient restrictions done as a result of this matching will be described. For each patient characteristic, the prevalence (categorical variables) or mean (continuous variables) will be calculated in each cohort. Absolute standardized differences, the difference in means or proportions divided by the pooled standard deviation, will be computed for each covariate to check its distribution balance within exposure groups (Annex 1: Table 3). For covariates with an absolute standardized difference greater than 0.10, residual differences will be further controlled in the analysis by including the specific variables in the Cox proportional hazards regression model.

#### PFIZER CONFIDENTIAL

# 9.7.2. Descriptive Analyses

Duration of baseline period (Annex 1: Table 2), duration of follow-up and reason for censoring will be described for each cohort (Annex 1: Table 4). Descriptive statistics will be presented to characterize the PS-matched exposed and comparator groups in terms of demographic information and medical history during the baseline period (Annex 1: Supplemental Tables 1 and 2; Tables 2-1 and 2-2). Specific characteristics of interest are described in Section 9.3 Variables. Counts and percentages for categorical data, and statistics such as mean, median, standard deviation, interquartile range, and range for continuous variables will be reported. Prior use and the duration of prior use of hormone therapy will be characterized for each cohort (Annex 1: Tables 2-1 and 2-2). Characteristics of LDVE use, including active ingredient, index formulation, duration of use, number of dispensings, number of dispensings per formulation (Annex 1: Table 3).

Incidence rates (IRs) and 95% confidence intervals (CIs) of endometrial cancer will be presented for each of the matched study cohorts, along with the number of events, total number of individuals, and accrued person-time. Incidence rates will be calculated as the number of incident events of endometrial cancer within the follow-up period divided by the total person-time at-risk (Annex 1: Table 5).

# 9.7.3. Comparative Analyses

Cox proportional hazards regression will be used to estimate hazard ratios (HRs) and 95% CIs.

#### 9.7.3.1. Primary Analysis

The primary analyses will estimate and compare the IR of endometrial cancer in postmenopausal women aged  $\geq 50$  years with a uterus regardless of prior use of hormone therapy in the following PS matched cohorts: (Annex 1: Table 5).

- a. New users of LDVE versus non-users of vaginal estrogen.
- b. New users of MDVE versus non-users of vaginal estrogen.
- c. New users of HDVC versus non-users of vaginal estrogen (HIRD only).

Person-time for treatment groups will begin after a six-month induction period and include any subsequent follow-up time until a censoring event occurs. Person-time for non-users will begin the day after their index date and continue until a censoring event.

#### **Subgroup Analyses**

A subgroup analysis will be conducted by prior use of estrogen and/or progestin hormone therapy (Annex 1: Table 5). In this subgroup analysis, assuming there is a sufficient sample size, the incidence of endometrial cancer will be compared in LDVE vs non-users, MDVE vs non-users, and HDVC vs non-users by the following types of prior hormone therapy:

• Unopposed estrogen

#### PFIZER CONFIDENTIAL

- Unopposed progestin
- Progestin opposed estrogen hormone therapy
- Other opposed estrogen hormone therapy
- No prior hormone therapy

Prior use of these medications will be measured using the entire baseline period.

The following subgroup analyses will be conducted separately among the PS-matched cohorts of new users of LDVE, MDVE, and HDVC and non-users of vaginal estrogens to determine if the HR of endometrial cancer varies by the following covariates (Annex 1: Tables 3 and 6):

- Active ingredient at the cohort entry date:
  - Estradiol vaginal;
  - Conjugated estrogen vaginal.
- Formulation at the cohort entry date:
  - Vaginal cream;
  - o Vaginal ring;
  - Vaginal tablet;
  - Vaginal insert.
- Duration of use.
- Number of dispensings.
- Number of dispensings per formulation

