### Primary Objectives:

- 1. To estimate and compare the IR of endometrial cancer in postmenopausal women aged  $\geq$ 50 years, with a uterus, regardless of prior use of hormone therapy (defined as any estrogen, progestin, E+P HT use or other opposed estrogen hormone therapy), in the following groups:
  - a. New users of low-dose vaginal estrogen (LDVE) versus non-users of vaginal estrogen;
  - b. New users of moderate-dose vaginal estrogen (MDVE) versus non-users of vaginal estrogen;
  - c. New users of high-dose Premarin Vaginal Cream (HDVC) versus non-users of vaginal estrogen (HIRD only, as Premarin VC is not marketed in Sweden)
- 2. To estimate and compare the IR of endometrial cancer separately among the LDVE, MDVE, and HDVC new users (HIRD only) aged ≥50 years, with a uterus, and regardless of prior use of hormone therapy relative to non-users of vaginal estrogen stratified by prior use of hormone therapy including unopposed estrogen, unopposed progestin, single-entity or combination progestin-opposed estrogen therapies, other opposed estrogen hormone therapies, or no prior hormone use.
- 3. To estimate and compare the IR of endometrial cancer separately among new users of LDVE, MDVE, and HDVC (HIRD only) aged ≥50 years, with a uterus, and regardless of prior use of hormone therapy relative to non-users of vaginal estrogen stratified by duration of use, formulation, active ingredient, number of dispensings and number of dispensings per formulation.

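### Formulation- and ingredient-specific HRs (LDVE, and MDVE in HIRD) are open to confounding because matching and balance checks are set only at dose-group level

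*Protocol*

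**What the plan says.** Protocol Section 8, Primary Objective 3, asks for comparisons of each dose group "relative to non-users of vaginal estrogen stratified by duration of use, formulation, active ingredient" and dispensing counts. Section 9.7.3.1 (Subgroup Analyses) carries this out in analyses "conducted separately among the PS-matched cohorts of new users of LDVE, MDVE, and HDVC and non-users of vaginal estrogens". It lists two active ingredients and four formulations (cream, ring, tablet, insert), each taken at cohort entry.

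The matching is described in Section 9.7.1. The score is the probability of being dispensed a drug in a dose group (LDVE, MDVE or HDVC). "Comparison groups will be individually matched to exposure groups according to PS", the aim being "to balance the exposure and comparator group on baseline risk factors for outcome at cohort entry", and "a matching ratio of 1:4 exposed (e.g., LDVE) to comparator patients (e.g., non-users) is planned".

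Absolute standardized differences are "computed for each covariate to check its distribution balance within exposure groups". Section 9.1.2 uses the term exposure group for the three dose groups. "For covariates with an absolute standardized difference greater than 0.10, residual differences will be further controlled in the analysis", by entering those covariates in the Cox model.

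The protocol states no propensity score, re-match, balance check or adjustment for a formulation or ingredient stratum. In the Annex 1 list, Table 2-2 covers characteristics of users and non-users after matching, and Table 6 covers incidence by characteristic of use. No title refers to balance by formulation.

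**The concern.** Formulation and ingredient are attributes of the drug dispensed, so a non-user belongs to no stratum. A score for receipt of any LDVE product balances the LDVE users as a whole against their comparators. It does not guarantee that ring, tablet, insert and cream users are each balanced. A whole-cohort standardized difference below 0.10 can hide opposite imbalances in two strata.

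These HRs answer a primary objective. Section 7 says the sponsor received a separate post-marketing requirement for its ring and for its cream. In the LDVE group, results for the ring and for low-dose cream can come only from strata. If users of one formulation have a different baseline risk, an apparent product difference could arise with no drug effect.

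**Working it through.** **1. Which groups are mixed** (Sections 9.1.2 and 9.2.1)

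| Group | Products | Mixed by formulation | Mixed by ingredient |
|---|---|---|---|
| LDVE, HIRD | Estring, estradiol tablets and insert, low-dose Premarin VC | yes | yes |
| LDVE, Sweden | Oestring, Vagifem | yes | no |
| MDVE, HIRD | estradiol and conjugated-estrogen dose bands both defined | yes | yes |
| MDVE, Sweden | 25 mcg Vagifem only | no | no |
| HDVC, HIRD | Premarin VC only | no | no |

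In the last two rows the stratum is the whole dose group, so the matching is already product-specific.

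**2. The plan's own figures.** There is none for these strata. The overall sizing reproduces: (1.960 + 0.842)² / (0.2 × 0.8 × (ln 1.5)²) = 298.4, so 299 events, against the stated 60 + 239 = 299. It does not bear on confounding.

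**3. Bias if a stratum is compared with all matched non-users.** All inputs here are assumptions, since the documents give no covariates by formulation. Take two formulations A and B, a true HR of 1, and one binary risk factor with relative risk RR. Its prevalence is pA and pB, and A's share of users is s. Mean risk is proportional to f(p) = 1 + p(RR − 1). The matched non-users have the pooled prevalence p = s·pA + (1 − s)·pB. The apparent HRs are f(pA)/f(p) and f(pB)/f(p).

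| s | pA, pB | RR | HR for A | HR for B |
|---|---|---|---|---|
| 0.5 | 0.30, 0.30 | any | 1.00 | 1.00 |
| 0.5 | 0.25, 0.35 | 1.5 | 1.125/1.15 = 0.98 | 1.175/1.15 = 1.02 |
| 0.5 | 0.25, 0.35 | 3 | 1.5/1.6 = 0.94 | 1.7/1.6 = 1.06 |
| 0.5 | 0.20, 0.40 | 1.5 | 1.10/1.15 = 0.96 | 1.20/1.15 = 1.04 |
| 0.5 | 0.20, 0.40 | 3 | 1.4/1.6 = 0.88 | 1.8/1.6 = 1.13 |
| 0.3 | 0.20, 0.40 | 3 | 1.4/1.68 = 0.83 | 1.8/1.68 = 1.07 |

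**4. Does keeping each user's own matched non-users remove it?** This was simulated in 4 million women with two binary covariates X1 and X2, each with prevalence 0.3. The logit of any use is −2.5 + a1·X1 + a2·X2. Among users, the logit of formulation A is g1·X1 + g2·X2. Comparator risk is the mean among non-users with the same pooled score, and the true HR is 1.

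| a1, a2 | g1, g2 | RR for X1, X2 | All matched non-users (A/B) | Own matched sets (A/B) |
|---|---|---|---|---|
| 0.7, 0.3 | −0.8, 0 | 2, 1.5 | 0.92/1.06 | 1.00/1.00 |
| 0.7, 0.7 | −0.8, 0.8 | 2, 1.5 | 0.97/1.03 | 0.97/1.03 |
| 0.7, 0.7 | −0.8, 0.8 | 2, 1 | 0.93/1.07 | 0.93/1.07 |
| 0.7, 0.3 | 0, 0 | 2, 1.5 | 1.00/1.00 | 1.00/1.00 |

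In the first row the pooled score separates women by X1, and keeping matched sets removes the bias. In the second and third rows, women with X1 only and women with X2 only share one score. A formulation can then differ on X1 and X2 within the same score, so the bias stays. Matched sets help but do not guarantee balance.

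**The case against.** Four points can be made for the plan.

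- **Choice of comparator.** A reader might infer that each formulation will be set against every non-user matched to the dose group. The text does not say so. Individual 1:4 matching equally allows each stratum to keep its own matched non-users. This stands, and the point therefore does not rest on that reading: step 4 shows that balance is not guaranteed either way.
- **Deferral to the SAP.** Section 9.7.1 leaves the details of estimation and matching to the SAP. It also cites a methods paper whose title concerns full-cohort propensity scores in subgroup analyses. Both are relevant. But Section 9.7.3.1 already fixes these analyses inside the dose-group cohorts, and a full-cohort score does not guarantee balance for a subgroup that is undefined among comparators.
- **Balance rule.** One might infer that the 0.10 rule can never act within a stratum. Section 9.7.1 does not forbid that; it is silent on strata.
- **Size.** An age gradient gives a more striking figure. If incidence rose 2% to 4% per year of age and one formulation's users were 9 years older than the LDVE average, the HR would read exp(0.02 × 9) = 1.20 to exp(0.04 × 9) = 1.43. The documents support neither input. With two equally used formulations, 9 years from the pooled mean implies 18 years between them.

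**Conclusion.** The concern holds in a limited form. For LDVE (formulation in both databases, ingredient in HIRD) and for MDVE in HIRD, the stratum-specific HRs are open to confounding, because balance is neither ensured nor checked where the comparison is made.

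A reader might go further and conclude that every formulation-specific HR is confounded. The documents do not support this. HDVC and Swedish MDVE are single-product groups. Elsewhere, bias arises only if formulation users differ on risk factors for endometrial cancer, and the protocol has no data on that.

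The size is therefore unknown. Under the assumed differences above, a true HR of 1.0 reads about 0.9 to 1.1, with extremes of 0.83 and 1.13 at a risk-factor RR of 3 and prevalences of 20% and 40%. It reads 1.0 if formulation users do not differ. This is modest beside the HR of 1.5 for which the study is sized, but it could matter when products are compared with each other.

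**What to change.** In Section 9.7.3.1 (Subgroup Analyses), for LDVE and for MDVE in HIRD:

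1. State that each formulation or ingredient stratum is compared only with the non-users individually matched to the exposed women in that stratum.
2. Report standardized differences within each stratum, and apply the 0.10 rule there by adjusting in the Cox model.
3. Where imbalance persists, re-estimate the propensity score for that stratum and re-match it against the full non-user pool.

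This takes protocol or SAP text and reruns of existing code, with no new data.

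The precision cost of item 1, relative to using all matched non-users, can be approximated. Assume a true HR of 1, equal follow-up, 1:4 matching and a stratum with share s of the exposed events. The variance of the log HR is then proportional to 1/s + 1/(4s) instead of 1/s + 1/4. For s = 0.5 the standard error rises by √(2.5/2.25) = 1.05, and for s = 0.3 by √(4.167/3.583) = 1.08. For very small strata the limit is √1.25 = 1.12.

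Re-matching may leave a few exposed women unmatched in small strata. It also makes the comparator populations differ between strata, so HRs from re-matched strata should be compared with each other cautiously.

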#### 9.7.3.2. Secondary Analyses

Like the primary analysis, Cox proportional hazards models will be used to estimate the HRs and 95% CIs for the following PS-matched cohorts of subjects with no prior use of hormone therapy (Annex 1: Table 5):

- a. LDVE new users versus E+P HT new users of hormone therapy.
- b. MDVE new users versus E+P HT new users of hormone therapy.

#### PFIZER CONFIDENTIAL

c. HDVC new users versus E+P HT new users of hormone therapy (HIRD only).

# 9.7.4. Sensitivity Analyses

Several sensitivity analyses will be conducted. Results from analyses conducted in the HIRD and Sweden will be pooled.

- HIRD and Sweden: The impact of various induction periods on the HR estimates will be assessed by calculating IRs and HRs for LDVE users and nonusers using no induction period, and an induction period of 3 months (lagging the start of follow-up for the LDVE group), and 12 months (Annex 1: Table 7 and 12). Additionally, the impact of lagging the start of follow-up for the non-user group will be assessed. LDVE users will be compared to nonusers with a six-month induction period for both groups.
- 2. HIRD and Sweden: To evaluate the possibility of informed censoring and selection in the main analysis resulting from the inclusion of multiple treatment episodes, a sensitivity analysis restricting follow-up to the first treatment episode will be conducted (Annex 1: Table 8 and 12). The HR of endometrial cancer will be calculated implementing censoring upon restart of index drug. The rationale is that the decision about whether or not to restart treatment could be influenced by past treatment experience. The comparison will be done for the following cohorts:
  - a. LDVE users versus non-users.
  - b. MDVE users versus non-users.
  - c. HDVC users versus non-users (HIRD only).
  - d. LDVE new users versus E+P HT new users.
  - e. MDVE new users versus E+P HT new users.
  - f. HDVC new users versus E+P HT new users (HIRD only).
- 3. HIRD and Sweden: An intent-to-treat (ITT) analysis will be conducted for the possibility of informed censoring and selection in the main analysis resulting from censoring on switching treatment. The ITT analysis will consider patients at risk during the entirety of their follow-up, regardless of discontinuing, or switching treatment, until the earliest of a diagnosis of endometrial cancer, a hysterectomy procedure, health plan disenrollment (HIRD only), emigration (Sweden only), death, or end of study. The HRs will be calculated comparing LDVE users to non-users, and, if sample sizes allow, stratified by prior use of hormone therapy. (Annex 1: Table 8 and 12).
- 4. HIRD and Sweden: The HR of endometrial cancer will be calculated without censoring on dispensing of a non-study progestogen (except contraceptives) to inform magnitude of changes on effect estimates should censoring be informative. The comparison will be done for the PS-matched LDVE users cohort versus non-users (Annex 1: Table 8 and 12).

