### 9.1.1. Time Periods

The study period, i.e., the beginning of the baseline period to the end of the follow-up period, is 01 January 2006 (earliest available date) through 31 December 2020 (or most recent available date) in the HIRD, and 01 January 1997 (earliest available date for medical record history) through 31 December 2019 (or most recent available date) in the Swedish registers. The difference between the two data sources in end of study dates is due to the difference in the lag time for populating the HIRD and the Swedish registers.

Ascertainment of exposure and follow-up will be 01 January 2007 - 31 December 2020 (or most recent available date) in the HIRD, and 01 July 2007 - 31 December 2019 (or most recent available date) in the Swedish Registers to allow for a 12- or 24-month baseline period in the HIRD and Swedish data bases, respectively. The index date is the day of initiating a study drug or, for non-users, the date of a gynecological visit that meets all inclusion and exclusion criteria. For new users of vaginal estrogens and E+P HT, a 6-month induction period is allowed following initiation of exposure and prior to beginning follow-up to allow for induction and diagnosis of endometrial cancer (Figure 1). For non-users, follow-up and accrual of person-time starts the day after the index date. The unexposed period before a woman starts any vaginal estrogen will be included as time at risk for a non-user until they begin using one of these drugs. The unexposed time at risk (non-users) will be censored if and when they start using vaginal estrogen, E+PHT or other non-study estrogen or progestogen medications. A sensitivity analysis is included that varies the length of the induction period and includes an induction period for the non-user cohort. Table 1 summarizes the different time periods for the two data sources. Patients may differ in their follow-up dates depending on when they meet the study inclusion, exclusion, and censoring criteria.

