  - The unexposed period before a woman starts any vaginal estrogen will be included as time at risk for a non-user until they begin using one of these drugs. The unexposed time at risk (non-users) will be censored when they start using vaginal estrogen, E+P HT or other non-study progestin or estrogen medications.
- Secondary Comparator: New Users of E+P HT.
  - Women who had  $\geq 1$  dispensing of E+P HT during the exposure ascertainment period, and no prior dispensings of any hormone therapy (excluding contraceptives).

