# 9.2. Setting

The study population consists of women in the HIRD and Sweden who are at least 50 years of age. For subjects using a vaginal estrogen or E+P HT, cohort qualification status will be assessed for the first study drug dispensing (index date) during the exposure ascertainment period (see Table 1) based on the inclusion and exclusion criteria described below. For the purpose of the primary objective, non-users of vaginal estrogen, subjects with at least one gynecological visit after age 50 and without any prior or current use of vaginal estrogens at the time of their gynecological visit (index date for non-users) will be included in this population regardless of their prior use of hormone therapy. Subjects may have multiple qualifying gynecological visits. For the purpose of the secondary objective, E+P HT new users with no prior use of hormone therapy will be included.

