### PFIZER CONFIDENTIAL

day after their index date (i.e., the date of a gynecological visit that meets all inclusion and exclusion criteria). Follow-up for all subjects will extend through the earliest of the following censoring events:

- Hysterectomy;
- Endometrial cancer;
- Dispensing of an estrogen hormone therapy product not included as a study drug (single-entity or combination, vaginal or non-vaginal formulation)
- Dispensing of a progestogen hormone therapy product not included as E+P HT (single-entity or combination, vaginal or non-vaginal formulation);
- End of continuous health plan eligibility (HIRD only);
- Emigration from Sweden (Sweden only);
- Death;
- End of the study period.
- Dispensing of a study drug that is in a different treatment group than the index treatment group, i.e., switching between LDVE, MDVE, HDVC, or E+P HT treatment groups;

Additional censoring criteria for non-users only:

• Dispensing of any study drug, which are defined in Section 9.2.1 Inclusion Criteria.

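### The ITT sensitivity analysis also drops the censoring of non-users who start LDVE, so one woman's LDVE time and cancer can count in both arms

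*Protocol*

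**What the plan says.** **Two records for one woman.** Protocol 9.1.2 states: "The unexposed period before a woman starts any vaginal estrogen will be included as time at risk for a non-user". For entry to the drug cohorts, 9.2 says that "cohort qualification status will be assessed for the first study drug dispensing (index date) during the exposure ascertainment period". The use-based exclusion for vaginal estrogen new users in 9.2.2 is a prior vaginal estrogen dispensing. Having been a non-user is not a bar.

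**What separates the records in the main analysis.** Section 9.1.1 says: "The unexposed time at risk (non-users) will be censored if and when they start using vaginal estrogen". In 9.2.3 this appears under its own heading of additional criteria for non-users only: "Dispensing of any study drug, which are defined in Section 9.2.1 Inclusion Criteria". Switching among LDVE, MDVE, HDVC and E+P HT is a separate entry in the general list.

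**What item 3 of 9.7.4 does.** Its stated aim is to examine informative censoring that results from censoring on switching treatment. The rule is: "The ITT analysis will consider patients at risk during the entirety of their follow-up, regardless of discontinuing, or switching treatment". Women are followed in this way "until the earliest of a diagnosis of endometrial cancer, a hysterectomy procedure, health plan disenrollment (HIRD only), emigration (Sweden only), death, or end of study". A study drug dispensing is not on that list. The comparison is then specified: "The HRs will be calculated comparing LDVE users to non-users, and, if sample sizes allow, stratified by prior use of hormone therapy".

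**The concern.** Item 3 is aimed at one censoring rule, but its list of end points removes two. Once non-users are no longer censored when they start, nothing in the text assigns a later LDVE starter to one arm, bars her from the LDVE arm, or keeps her post-start time out of the comparator arm.

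Two separate things follow. First, the comparator arm contains LDVE-exposed time, which attenuates any non-null HR. Second, the same woman and the same cancer can sit on both sides of the ratio, so the arms are no longer independent.

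The analysis is meant to show whether censoring distorts a safety estimate. If its HR is lower than the main one, a reader could take that as reassurance about informative censoring when part of the fall comes from how time is allocated.

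**Working it through.** **1. The plan's own figure.** The protocol gives no figure for the ITT analysis. Its HIRD study size (9.5.1) reproduces with the Schoenfeld formula at two-sided alpha 0.05, 80% power, HR 1.5 and 1:4 allocation:

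(1.960 + 0.842)² / [0.2 × 0.8 × (ln 1.5)²] = 298.4, rounded up to 299, as stated (60 + 239).

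The stated person-years times the background rate give the same: (80,105 + 320,410) × 0.000745 = 298.4. The inputs can therefore be reused.

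**2. The two rules applied to one illustrative record.** Gynecological visit January 2010, LDVE start January 2013, cancer January 2015.

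| Rule | Non-user record | LDVE record |
|---|---|---|
| Main analysis | 3 years, no event | 1.5 years, event |
| Item 3 as written | 5 years, event | 1.5 years, same event |

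The LDVE record starts six months after dispensing (9.2.3). Those six months count in the non-user arm only.

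**3. Effect on the HR, HIRD.** Inputs from 9.5.1: 152,941 LDVE users, 611,764 non-users, 2.4 years, 74.5 per 100,000 person-years. Let p be the share of LDVE women who also hold a matched non-user record (assumed; the protocol gives no figure). Each such woman adds 0.5 + 2.4 = 2.9 years to the comparator arm, of which 2.4 carry the LDVE hazard.

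- Non-user person-time = 611,764 × 2.4 + p × 152,941 × 2.9
- Non-user events ÷ background rate = 611,764 × 2.4 + p × 152,941 × (0.5 + 2.4 × HR)
- ITT HR = true HR ÷ (second line ÷ first line)
- LDVE cancers at HR 1.5 = 152,941 × 2.4 × 1.5 × 0.000745 = 410; shared cancers = p × 410

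| p | Person-time | Events ÷ rate (HR 1.5) | Ratio | ITT HR, true 1.5 | Shared cancers | ITT HR, true 2.0 |
|---|---|---|---|---|---|---|
| 10% | 1,512,586 | 1,530,939 | 1.012 | 1.48 | 41 | 1.95 |
| 25% | 1,579,116 | 1,624,998 | 1.029 | 1.46 | 103 | 1.89 |
| 50% | 1,689,998 | 1,781,763 | 1.054 | 1.42 | 205 | 1.80 |

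At a true HR of 1.0 the two lines are equal and there is no bias.

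**4. Second parameterisation.** Let q be the share of non-user ITT person-time that falls after LDVE start. Then ITT HR = HR ÷ [(1 − q) + q × HR]. For HR 1.5, q of 5%, 10% and 20% give 1.46, 1.43 and 1.36. With assumed LDVE start rates of 1% to 10% per year, q is 1.2% to 11.1% over 2.4 years and 2.5% to 21.3% over 5 years.

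**5. Simulation.** Start rate 5% per year, 5 years of follow-up, six-month lag, true HR 1.5, and a tenfold background rate for precision. The rate ratio was 1.49 with non-users censored at start and 1.43 under item 3. Of the non-user cancers, 13.3% (30,402 of 228,999) also counted in the LDVE arm, as did 9.3% of non-user person-time.

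**6. Variance.** With d1 LDVE events, d0 non-user events and m shared, the approximate variance of the log ratio is 1/d1 + 1/d0 − 2m/(d1 × d0). The naive version omits the last term. In the simulation the naive SE was 0.0061 and the SE allowing for overlap 0.0053. With the step 3 figures at HR 1.5:

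- p = 10% (d1 = 410, d0 = 1,530,939 × 0.000745 = 1,141, m = 41): 0.058 naive, 0.056 with overlap.
- p = 50% (d0 = 1,781,763 × 0.000745 = 1,327, m = 205): 0.056 naive, 0.049 with overlap.

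**The case against.** **Dilution is what an ITT analysis accepts.** Item 3 openly follows women regardless of switching, and time on LDVE in the comparator arm is ordinary contamination. This stands as to mechanism. A reader might infer that counting the cancer twice is what pulls the HR towards 1, but the arithmetic does not support that. Only the non-user rate changes in step 3, and the attenuation would be there if no woman appeared twice. Duplication contributes only the dependence between arms. Ordinary ITT does, however, assign each person once, and item 3 does not.

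**The text may not mean this.** Section 9.2.3 treats switching and non-user initiation as separate rules, and 9.1.1 counts a woman as a non-user only up to her first vaginal estrogen. On that reading non-users are still censored at start in item 3. But item 3 gives its own closed list, which replaces the main censoring rules and omits study drug dispensing. At best the two readings compete and the protocol must choose.

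**Variance is SAP material.** The choice of estimator is. The rule that lets one woman enter both arms is fixed in the protocol.

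**The size is small and assumed.** This is fair. With 410 LDVE and 1,094 non-user events the SE of the log HR is about 0.058. The shift in log HR is 0.012 at 10% overlap and 0.053 at 50%, below one SE even there. Step 3 also gives each overlapping woman 2.9 years beyond 2.4 non-user years, which favours a larger effect.

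**Censoring non-users at start weakens the test.** It puts potentially informative censoring back into one arm. This stands, and is why that version should accompany the uncensored one and not replace it.

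**Conclusion.** The point holds as a minor one. As written, item 3 removes the non-user censoring rule along with the switching rule it means to test, and lets one woman's post-induction LDVE time and cancer count in both arms. For a true HR of 1.5 the expected result is about 1.48, 1.46 or 1.42 at 10%, 25% or 50% overlap, and unchanged at HR 1.0.

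This rests on an assumed overlap. Duplication also requires both of the woman's records to be in the propensity-matched set and the drug started to be LDVE.

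Three stronger conclusions that a reader might draw are not supported:

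- *The confidence interval is too narrow.* In the simulation and in step 6 the shared events make the naive interval too wide.
- *The HR always moves towards 1.* Cancers in the first six months after LDVE start count in the non-user arm only, so an excess of early diagnoses there could push the HR below 1.
- *The study's main result is affected.* The primary analysis censors non-users at initiation. At the available HIRD size, power also stays above 97% even with 30% of non-user time after LDVE start, so the issue is interpretation of one sensitivity analysis.

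**What to change.** In 9.7.4 item 3:

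1. State explicitly how a non-user who starts LDVE is handled.
2. If non-users stay uncensored, use a variance clustered by woman and report how many cancers and how much person-time appear in both arms.
3. Present alongside it a version that ends the non-user record at the first vaginal estrogen dispensing, while dropping censoring for discontinuation, switching between treatment groups and dispensing of other hormones.
4. Add that a lower HR in the uncensored version cannot by itself be read as evidence against informative censoring.

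Clustering and overlap counts make the duplication visible but do not remove the attenuation, so the parallel version is needed to judge it. The cost is a few sentences, one programming condition and one extra run of a sensitivity analysis. The downside is that censoring at initiation remains in the non-user arm of the parallel version.
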